7.5 Medical and Surgical History

Medical and surgical history will be coded using MedDRA version 22.0. The number and percentage of subjects with a medical history event will be summarized descriptively using the Safety Population. The table will be sorted in descending order of MedDRA system organ class (SOC) and within each SOC by descending frequency of preferred terms (PT) in the Total column (all subjects pooled). A by-subject listing will also be created.

7.6 Medications

All medications will be coded using WHO Drug Dictionary (WHODrug Global B3 March 2019 version). Medications will be summarized by Anatomic Therapeutic Class (ATC) level 2 terms (ATC2) and ATC level 4 (ATC4) terms using the Safety Population. Subjects will be counted only once for each ATC2 or ATC4 term in the event that they have multiple records of the same ATC level in the database. The table will be sorted by the descending order of frequencies of ATC2 terms and within each ATC2 by the descending order of frequencies in ATC4 terms in the Total column (all subjects pooled). By-subject listings will also be created.

7.6.1 Prior Medications

Prior medications are defined as those medications with a start date prior to the first dose date of study drug. Prior medications will be summarized in a table and presented in a by-subject listing.

7.6.2 Concomitant Medications

Concomitant medications are defined as those medications taken on or after the date of first dose of study drug, including any medications that were started before the first dose date of study drug and are ongoing. Concomitant medications will be summarized descriptively and presented in a by-subject listing.

Note that a medication can be both prior and concomitant depending on the start and stop date as related to the first dose date of study drug.

8 Efficacy

All efficacy analyses will be performed using the Efficacy Population. Results will be summarized in a table for the pooled Placebo group, EQ001 treatment group from each Cohort and pooled EQ001 treatment groups from all cohorts.

8.1 Secondary Endpoints Analyses

8.1.1 Change from Baseline in Serum IgE Levels

The actual and change from Baseline values of serum IgE levels will be presented using continuous descriptive summary statistics at each post-Baseline visit. Box and whisker plots of change from baseline by nominal post-baseline visit will also be created. A by-subject listing will be created.

8.1.2 Change from Baseline in Total Eosinophil Count

The actual and change from Baseline values of total eosinophil count will be summarized by visit in a table, using continuous descriptive summary statistics. Box and whisker plots of change from baseline by nominal post-baseline visit will also be created. A by-subject listing will also be created.

[REDACTED]

[REDACTED]

[REDACTED]

8.1.4 Change from Baseline in Prebronchodilator Pulmonary Function Test Parameters

Following pulmonary function test parameters recorded during the site visit using Masterscope will be summarized: FEV1 (L), FEV1 % PredictedFVC (L), FEV1/FVC (%), and PEFR (L/min).

The actual and change from Baseline values of the above parameters will be summarized by visit in a table, using continuous descriptive summary statistics. Box and whisker plots of change from baseline by nominal post-baseline visit will also be created for each of the above parameters. A by-subject listing will also be created.

8.1.5 Change from Baseline in FeNO

The level of FeNO will be measured in each subject at every study visit (other than Day 4) using a standardized single-breath FeNO test. Subjects will inhale to total lung capacity through the NIOX MINO® Airway Inflammation Monitor and then exhale for 10 seconds at 50 mL/sec (assisted by visual and auditory cues). The obtained value will be recorded, and the process will be repeated for a total of 2 measurements. For analysis purposes, the mean of the 2 non-missing measurements will be taken. The actual and change from Baseline values of FeNO will be summarized by visit in a table, using continuous descriptive summary statistics (n, mean, standard deviation (SD), median, minimum, and maximum) at Baseline and each post-Baseline visit. Box and whisker plots of change from baseline by nominal post-baseline visit will also be created. A by-subject listing will also be created.

8.1.6 Change from Baseline in Peak Expiratory Flow Rate and FEV1 Recorded on AM3 Device

Home pulmonary function testing to measure peak expiratory flow rate (PEFR) and FEV1 will be performed twice daily, in the morning upon awakening and in the evening before bedtime, using a peak

[REDACTED]

flow meter. Subjects perform 3 successive peak flow maneuvers at session to record FEV1 and PEFR; highest of the 3 values will be used in the analysis of each variable.

The diurnal variation of PEFR will be the amplitude percentage mean defined as: Diurnal variation in PEFR (%) = $100 \times |\text{Evening-Morning}|/\text{mean of the Morning and Evening values}$, where $|\cdot|$ indicates absolute value.

For data summarization purposes, an average value of the variable of interest (FEV1, PEFR, and Diurnal Variation of PEFR) will be calculated by study week (and for morning and evening for FEV1 and PEFR). Study Days 1 to 7 will be designate as Study Week 1, Study Days 8 to 14 will be Study Wek 2, etc. Similarly Study Days -7 to -1 will be assigned Study Week -1, Study Days -14 to -8 will be Study Week -2 etc. For this summary, baseline value will be considered as the average value calculated for Study Week -1. For example, baseline PEFR in the morning will be the average of the morning PEFR values recorded on Study Week -1 (i.e., Study Days -7 to -1).

The actual and change from Baseline values of PEFR and FEV1 assessed in the morning and evening and the calculated diurnal variation of PEFR, will be summarized by Study Week in a table, using continuous descriptive summary statistics. A by-subject listing will also be created.

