10.8 Home Peak Flow Testing

Home peak flow testing for peak expiratory flow rate (PEFR) will be performed twice daily, in the morning upon awakening and in the evening before bedtime, using a peak flow meter. PEFR will be recorded during the Screening, Treatment, and Safety Follow-up Periods in the eDiary. PEFR measurements should be taken at least 6 hours after the last dose of SABA rescue medication. Subjects should perform 3 successive peak flow maneuvers while the subject is sitting or standing, but the subject should be in the same position at every testing. The highest of the 3 values should be captured for each time point. At each study visit, the investigator or authorized delegate will check the subject's compliance with the peak flow measurements and confirm that the subject is using the peak flow meter correctly.

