13.1 General Considerations

Data will be summarized using descriptive statistics (n, mean, median, standard deviation, minimum, maximum) for continuous variables and frequencies and percentages for discrete variables. All data summaries will be displayed by cohort and by treatment group (EQ001 or placebo). A total column for treated cohorts separated by treatment group will also be included. Baseline values of variables are considered the last available non-missing value prior to receiving any study drug. By-subject listings of the data will also be provided. All data summaries and listings will be produced using the SAS® software, version 9.3 or higher.

[REDACTED]

[REDACTED]

[REDACTED]

[REDACTED]

[REDACTED]

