3.5 Treatment Assignment & Blinding

An interactive web response system (IWRS) will be used to ensure study drug inventory, accountability, and appropriate cohort allocation and blinded treatment assignment. The site's unblinded pharmacist or designee will have access to the IWRS and all treatment assignments.

After informed consent has been obtained, all screening procedures have been assessed, and study eligibility has been confirmed, subjects will be randomized to receive either EQ001 or placebo on Study Day 1. The unblinded study pharmacist or designee will access the IWRS to randomize the subject into the study, receive the unblinded treatment assignment and dose, record drug accountability, and request resupply. EQ001 will be administered Q2W for 8 weeks (a total of 5 doses) at the following dose levels:

- **Cohort 1:** Randomized 3:1 (EQ001: Placebo)
 - EQ001 0.8 mg/kg
 - Placebo
- **Cohort 2:** Randomized 3:1 (EQ001: Placebo)
 - EQ001 1.6 mg/kg
 - Placebo
- **Cohort 3:** Randomized 3:1 (EQ001: Placebo)
 - EQ001 2.4 mg/kg
 - Placebo
- **Cohort 4:** Randomized 3:1 (EQ001: Placebo)
 - EQ001 3.2 mg/kg
 - Placebo

[figure not shown]
EQ001 or placebo doses will be administered in the clinic; subjects will be observed for a minimum of 30 minutes after administration.

Investigators, site staff, and subjects will be blinded to treatment assignment. The Sponsor may be unblinded to treatment assignment. The unblinded pharmacist or designee will be instructed not to divulge the treatment administered to any subject with the blinded site personnel, study subject or blinded study monitor and any other blinded CRO/vendor team members.

[figure not shown]
The blind should be broken only if knowledge of the subject's treatment allocation would facilitate specific emergency treatment. Unblinding procedures are provided in the Pharmacy and IWRS Manuals. The investigator should contact the Sponsor and/or designee prior to unblinding a subject's treatment assignment. In the event of an emergency when unblinding is necessary and the Sponsor and/or designee could not be contacted, the investigator must contact the Sponsor and/or designee as soon as possible after the unblinding. Treatment assignment may be provided to the study sites/subjects after database lock.

Following final database lock all roles may be considered unblinded.

This document is confidential.

This document is confidential.

4 Endpoints

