6.2 Key Definitions

- **Relative study day:** A relative study day is a day of any study assessment relative to the first dose of study drug. The day of the first dose of the study drug will be considered as Day 1 (Visit Day 1 per protocol). Pre-treatment and on-treatment study days are numbered relative to the day of the first dose of study drug. The preceding day of the first dose of the study drug will be considered as Day -1 and next day after the first dose of the study drug will be considered as Day 2 and so on. There will not be a study day of Day 0.
- **Baseline Value:** Unless indicated otherwise, baseline value of a variable is defined as the last non-missing value on or prior to the first dose of study drug. If there are two values qualifying for the baseline value (e.g., FeNO measurements are taken in duplicate), the average of the two will be considered as the baseline value.

This document is confidential.

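### SAP 8.1.6 averages the pre-dose Day 1 awakening PEFR and FEV1 into on-treatment Study Week 1, so the expected Week 1 morning change is diluted by about one seventh with full diary data

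*SAP*

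**What the plan says.** Under SAP 8.1.6, home PEFR and FEV1 are measured "twice daily, in the morning upon awakening and in the evening before bedtime". Weekly averages are then formed, with morning and evening kept apart for both measures, and diurnal variation of PEFR is averaged by week as well. The windows are whole calendar days: "Study Days 1 to 7 will be designate as Study Week 1", and the baseline for this summary is the average over Study Week -1, Days -7 to -1.

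The timing of Day 1 comes from other sections:

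- SAP 6.2: "The day of the first dose of the study drug will be considered as Day 1". There is no Day 0.
- SAP 3.5: "subjects will be randomized to receive either EQ001 or placebo on Study Day 1", and "EQ001 or placebo doses will be administered in the clinic".
- Protocol 10.8: "PEFR will be recorded during the Screening, Treatment, and Safety Follow-up Periods in the eDiary". A Day 1 morning PEFR is therefore expected.
- Protocol 10.6: clinic spirometry is done before study drug is given and starts between 6 AM and noon.

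Protocol 13.1 gives the general baseline rule: "Baseline values of variables are considered the last available non-missing value prior to receiving any study drug". SAP 6.2 has a similar rule but allows exceptions, and 8.1.6 makes one.

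**The concern.** A reading taken at home on waking comes before a clinic dose given later the same day. The week rule nevertheless counts it as post-baseline. It cannot carry any drug effect, so averaging it with the later mornings mixes untreated and treated values.

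Change in PEFR is a listed secondary endpoint, and Week 1 is the first on-treatment row of the table, where early onset would be read. The evening average for the same week contains no pre-dose reading. The table could therefore show a small difference between morning and evening change that comes only from the window. The Day 1 diurnal value has a related defect: one half is pre-dose and the other post-dose, so it describes neither state.

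**Working it through.** The plan gives no figure to reproduce here. SAP 6.1 states that there is no formal hypothesis testing, and no effect size or speed of onset is given for home PEFR or FEV1. The check is arithmetic on the weekly mean.

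**Is the Day 1 morning reading pre-dose?** The session is on awakening (SAP 8.1.6). Day 1 is the calendar day of first dose (SAP 6.2). Randomization is on Day 1 and dosing is in the clinic (SAP 3.5), after clinic spirometry (Protocol 10.6). So the reading precedes the first dose.

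**Which window holds it?** Week 1 covers Days 1 to 7 and baseline covers Days -7 to -1, so it falls in Week 1.

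**Dilution of the morning change.** Let k be the number of recorded Week 1 mornings, Day 1 included, and let D be the mean change over the k - 1 post-dose mornings. Assume that the Day 1 reading equals the Week -1 mean on average, so its expected change is 0.

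Expected Week 1 morning change = [0 + (k - 1) × D] / k = D × (k - 1)/k, an attenuation of 1/k.

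| Mornings recorded, including Day 1 | Share of D kept | Attenuation |
|---|---|---|
| 7 | 6/7 = 85.7% | 14.3% |
| 6 | 5/6 = 83.3% | 16.7% |
| 5 | 4/5 = 80.0% | 20.0% |
| 4 | 3/4 = 75.0% | 25.0% |
| 3 | 2/3 = 66.7% | 33.3% |

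**In absolute terms** (D is assumed, as the documents give none), with all 7 mornings: D = 10, 20 or 30 L/min is reported as 8.6, 17.1 or 25.7 L/min.

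**Does the shape of onset matter?** With complete data and an effect rising linearly from 0 on Day 1 to its full Day 7 value, the 7-day mean is 0.500 of the Day 7 effect and the mean of Days 2 to 7 is 0.583. The ratio is 0.500/0.583 = 0.857, again 6/7.

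**Other summaries.** In the Week 1 evening averages, 0 of 7 readings are pre-dose. In the Week 1 diurnal average, 1 of 7 values mixes pre- and post-dose readings. Because that measure is an absolute difference, the direction of the distortion cannot be stated. From Week 2 onward no reading precedes the first dose.

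**The case against.** The strongest reply is that the consequence is very small. The summaries are descriptive, no visible text makes Week 1 a key time point, and the same window applies to placebo and to every EQ001 dose. Clinic FEV1 and PEFR are summarized by visit (SAP 8.1.4), with a Day 8 test, and by-subject listings are planned. All of this stands and sets the weight of the point.

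Three stronger readings are tempting, and the documents do not support them.

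- *Every subject's Week 1 change is pulled toward zero.* One noisy reading can move an individual mean either way, and a subject without a Day 1 morning reading has no dilution. The 1/k result is an expectation, and the 20% and 33% figures require Day 1 to be among the readings kept.
- *The rule biases the comparison in favour of EQ001.* The Day 1 reading precedes the first dose in all arms. For a given k, a between-group difference shrinks by the same fraction, so the rule does not create a false effect.
- *SAP 8.1.6 breaches the general baseline rule, so the reading must move into baseline.* Protocol 13.1 takes a single last value, whereas 8.1.6 openly defines a weekly average, which SAP 6.2 permits. The general rule does not prescribe an eight-reading mean.

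The centring assumption can also be questioned. Protocol 10.6 requires long-acting bronchodilators to be withheld for 12 to 24 hours before clinic spirometry, so the Day 1 awakening reading may be taken during a withhold that did not apply on most baseline days. If this lowers it by w on average, the expected Week 1 morning change becomes D × (k - 1)/k - w/k. The within-arm distortion is then not a pure shrinkage. This qualifies the percentages, and it also argues against putting the reading into baseline.

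Finally, the Schedule of Events, the Day 1 activities in Protocol Section 12 and SAP 6.3 are not in the public text. A rule there for the Day 1 home reading cannot be excluded.

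**Conclusion.** The point holds and is minor. On the visible text, a reading that precedes the first dose is averaged as on-treatment. The expected Week 1 morning change in PEFR and FEV1 is attenuated by 1/k, which is 14% with a complete diary and more with missing days. One of up to seven Week 1 diurnal values is a hybrid.

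The size rests on two assumptions: the Day 1 morning reading is present, and on average it equals the Week -1 mean. The absolute loss depends on how much change occurs in the first week, which the documents do not give. The fault is confined to the Week 1 morning and diurnal summaries. It does not touch Week 1 evening averages, Weeks 2 to 12 or any formal test.

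**What to change.** Add a sentence to SAP 8.1.6 stating that:

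- the Day 1 morning reading is pre-dose and is left out of Study Week 1, so that Week 1 morning averages of PEFR and FEV1 use Days 2 to 7 and evening averages use Days 1 to 7;
- the Day 1 diurnal pair is left out of the Week 1 average;
- the Week -1 baseline stays at Days -7 to -1.

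Exclusion is preferable to moving the reading into baseline. A move would give it a weight of 1/8 in the reference for every later week, set eight baseline mornings against seven evenings, and bring in any effect of the bronchodilator withhold. On the notation above, the baseline would fall by w/8 and the morning change in all later weeks would rise by w/8.

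No new data are needed. The cost is one fewer morning reading and one fewer diurnal value in the Week 1 averages; a subject whose only Week 1 morning reading is Day 1 would have no Week 1 morning value. The excluded reading remains in the by-subject listing.

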8.1.7 Change from Baseline in ACQ-6 score

The actual and change from Baseline in the ACQ-6 score will be summarized by visit using continuous descriptive summary statistics (n, mean, standard deviation (SD), median, minimum, and maximum) at Baseline and each post-Baseline visit. Box and whisker plots of change from baseline by nominal post-baseline visit will also be created. A by-subject listing will also be created.

The ACQ-6 score will be derived by taking the mean of the values of the 6 questions, each question is on a 7-point Likert scale (0=totally controlled, 6=severely uncontrolled).

The number and percent of subjects showing an improvement of ≥ 0.5 points (a minimally important difference, MID) from Baseline to each post-Baseline visit (i.e. the post-Baseline score – the Baseline score is ≤ -0.5) will be summarized by visit. Number and percentage of subjects achieving MID in ACQ6 score at any visit will also be summarized.

An ACQ-6 score of ≤ 0.75 indicates well-controlled asthma, $>0.75 < 1.5$ indicates partially controlled asthma and ≥ 1.5 indicates uncontrolled asthma. The number and percent of subjects belonging to each of the above categories will also be summarized by visit.

8.1.8 Time to First Asthma Exacerbation (any severity)

Time to first exacerbation in days is defined as time from the first dose date to the first observed exacerbation date and will be calculated as:

Time to first exacerbation (days) = date of first exacerbation – date of first dose + 1

Subjects who do not experience any exacerbation will be censored at the last contact date of the subject.

Time to first exacerbation will be analyzed using Kaplan-Meier methodology ([Kaplan & Meier, 1958](#)). If estimable, the median time to first exacerbation, 25th and 75th percentiles with 2-sided 95% confidence intervals (CIs) will presented. Number and percentage of subjects with exacerbation events will also be presented.

8.1.9 Asthma symptoms, use of controller (standard) and rescue medications, nighttime awakening due to asthma and asthma-related activity limitations – Responses to a Questionnaire (as recorded on an eDiary)

Subjects will be recording their responses to 6 morning questions and 9 evening questions daily related to their Asthma. The questions are as follows (MQ=Morning Question, EQ=Evening Question) with a brief description of possible responses:

A horizontal bar chart consisting of 15 solid black bars of varying lengths. The bars are arranged in a staggered, non-overlapping pattern, creating a sense of depth or sequence. The lengths of the bars range from approximately 10% to 100% of the total width of the chart area. The bars are set against a plain white background.

This document is confidential

8.1.10 Annualized Rate of Asthma Exacerbations (of any severity)

The number of asthma exacerbations will be calculated for each subject. A follow-up duration in years for each subject will be calculated as:

Follow-up duration (years) = (last contact date – date of first dose + 1) / 365.25, rounded to 2 decimal places.

The annualized rate of asthma exacerbations i.e. number of asthma exacerbation per subject year will be calculated as total number of asthma exacerbations for all subjects / total follow-up duration in years for all subjects.

Rate of asthma exacerbation will be tabulated, and a by-subject listing of all exacerbations will be created.

In addition, duration of asthma exacerbations in days is calculated as (the end date – the start date)+1. If asthma exacerbation is ongoing, the missing end date will be imputed as last known visit date. If a subject has multiple asthma exacerbations, each event will be counted separately.

The primary criterion for asthma exacerbations will also be summarized by criterion in number and frequency format. All asthma exacerbations will be included in this summary, a subject may have more than one exacerbation event.

[REDACTED]

[REDACTED]

[REDACTED]

[REDACTED]

[REDACTED]

[REDACTED]

This document is confidential.

[REDACTED]

10 Safety

All safety analyses will be performed using the Safety Population.

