2. **Treatment Period:** Will begin on Day 1 with the first study drug dose and have a duration of 8 weeks. During the Treatment Period, 5 doses of study drug will be administered SC, 1 dose each on Study Days 1, 15, 29, 43, and 57. Subjects will return to the study site for follow-up evaluations according to the Schedule of Events (SOE). Following the last dose of study drug, subjects will enter the Safety Follow-up Period.
3. **Safety Follow-up Period:** Will have a 4-week duration and conclude 4 weeks after the final study drug dose with the End-of-Study (EOS) Visit on Day 85.

Successive cohorts that are randomized in a 3:1 ratio (active:placebo) will be enrolled. Subjects will be treated Q2W for 8 weeks and followed for a total of 12 weeks after the initial study drug dose on Day 1. [REDACTED]

[REDACTED] Randomization in the next dose cohort will not begin until the Data Review Committee (DRC) review of all available safety data from all subjects supports escalation to the next dose level. The MTD of EQ001 in subjects with moderate-to-severe uncontrolled asthma will be determined based on all available data, including safety, tolerability, PK, PD, and clinical activity data.

[REDACTED]

[REDACTED]

If subjects do not complete the required study visits or discontinue from the study for any reason, they will be asked to return to the clinical study site for an Early Termination (ET) Visit, as described in the SOE.

Study Procedures:

While on study, all subjects will take their standard medications for their moderate-to-severe asthma, as prescribed by the study physician. These standard medications will consist of a moderate- or high-dose inhaled corticosteroid (CS) and one or more additional controller medications (eg, inhaled long-acting beta agonist [LABA], or anticholinergic). Leukotriene antagonists (LTAs) may also be used as controller medications. Allergen immunotherapy at a stable dose is permitted, but monoclonal antibody (mAb) therapeutics are prohibited. Doses of all controller medications must be stable for 4 weeks including the duration of the Screening Period.

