10.5 Asthma Clinical Status Assessment

The investigator and/or designee will conduct an asthma clinical status assessment at specific time points, as specified in the SOE. These clinical status assessments will include:

- Pulmonary function test
- FeNO level measurement
- PRO assessment, ACQ-6

A history of *clinically significant asthma exacerbations* (defined as a $> 20\%$ decrease in AM or PM peak flow measurements sustained for 2 days, a doubling of the inhaled corticosteroid dose, initiation of an oral corticosteroid burst for asthma or an emergency department visit/hospitalization for asthma) will be obtained at each scheduled study visit (other than Day 4) and any unscheduled visits. Diary entries that meet the criteria for a clinically significant exacerbation should also be recorded in the eCRF.

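### The imputed end date for an ongoing exacerbation can fall before its start, and unresolved exacerbations are counted as finished at the last visit

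*SAP*

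**What the plan says.** SAP 8.1.10 mainly concerns the annualized rate, but it adds a duration for each event: "duration of asthma exacerbations in days is calculated as (the end date – the start date)+1". For events without an end date it says: "If asthma exacerbation is ongoing, the missing end date will be imputed as last known visit date". Its visible text sets no lower limit at the start date, does not mark the duration as censored, and does not turn to a later contact or diary date.

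Other rules in the SAP use a different end of observation. The rate denominator in the same section is "Follow-up duration (years) = (last contact date – date of first dose + 1) / 365.25". SAP 8.1.8 says: "Subjects who do not experience any exacerbation will be censored at the last contact date of the subject". Follow-up duration in SAP 7.1 also runs to the last contact.

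The protocol provides for exacerbations identified between visits. Section 10.5 says: "Diary entries that meet the criteria for a clinically significant exacerbation should also be recorded in the eCRF". Section 10.8 says: "PEFR will be recorded during the Screening, Treatment, and Safety Follow-up Periods in the eDiary". Section 10.9.1 adds that diary alerts tell a worsening subject to contact the investigator, which need not lead to a visit.

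On timing, Protocol 2.1 schedules "1 dose each on Study Days 1, 15, 29, 43, and 57", and the safety follow-up is to "conclude 4 weeks after the final study drug dose with the End-of-Study (EOS) Visit on Day 85". The visits listed there include none between Day 57 and Day 85.

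**The concern.** The imputation is anchored to visits, while events can be detected without one. A subject whose exacerbation begins after the last attended visit, and who is not seen again, has an onset later than the imputed end. The formula then returns zero or a negative number. The same event lies inside the follow-up used for the rate whenever the last contact is on or after onset, so two parts of one section would treat it inconsistently.

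A more ordinary problem needs no unusual sequence. Any event still active at the last visit is given that day as its end, so a duration known only to be at least so long enters as an observed one.

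The credibility of the duration summary is at stake. Each cohort has 8 subjects randomized 3:1, so about 6 on EQ001. The general methods in SAP 6.1 call for mean, SD, median, minimum and maximum. In groups of that size one impossible value can set the minimum and move the mean.

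**Working it through.** The documents give no figure for exacerbation duration, so there is none to reproduce. The check applies the SAP's formula to the protocol's visit schedule.

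**Inputs**
- Duration = end - start + 1, with end = last visit for ongoing events (SAP 8.1.10).
- Nominal visits on Days 1, 4, 8, 15, 29, 43, 57 and 85 (Protocol 2.1 and the list of Section 12 headings). Visit windows are ignored.
- Last contact date as the alternative end, as the SAP uses elsewhere. Contact dates and true end dates below are assumptions.

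**Onset after the last attended visit.** Let the last visit be day V and onset be day V + k. Then duration = V - (V + k) + 1 = 1 - k.

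With V = 57 and no later visit:

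| Onset day | k | SAP rule | End at last contact, assumed 3 days after onset |
|---|---|---|---|
| 58 | 1 | 57 - 58 + 1 = 0 | 4 |
| 59 | 2 | 57 - 59 + 1 = -1 | 4 |
| 64 | 7 | 57 - 64 + 1 = -6 | 4 |
| 70 | 13 | 57 - 70 + 1 = -12 | 4 |
| 84 | 27 | 57 - 84 + 1 = -26 | 4 |

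In a 14-day gap the lowest value is 1 - 13 = -12. In the 28-day gap from Day 57 to Day 85 it is 1 - 27 = -26. Onset on the visit day itself gives 1.

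**Onset before the last visit, unresolved**
- Onset Day 50, last visit Day 57: 57 - 50 + 1 = 8 days. With an assumed last contact on Day 70, still ongoing: 70 - 50 + 1 = 21 days, censored. If the true end were Day 75: 75 - 50 + 1 = 26 days.
- Completer, onset Day 80, ongoing at Day 85: 85 - 80 + 1 = 6 days. If last contact is also Day 85, a last-contact rule gives the same 6. If the true end were Day 92: 92 - 80 + 1 = 13 days. Here the date is reasonable, and the fault is only that 6 is recorded as complete.

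**Effect on a group mean (assumed data).** Take four resolved events of 8 days and one ongoing event with onset Day 64 after a last visit on Day 57.
- SAP rule: (4 × 8 - 6) / 5 = 5.2 days.
- End at last contact 3 days after onset: (4 × 8 + 4) / 5 = 7.2 days.
- Resolved events only: 32 / 4 = 8.0 days, with 1 event reported as ongoing.

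**What does not change.** The rate is the event count over follow-up to last contact. Time to first exacerbation uses the start date of the first event, or last contact if there is none. Neither uses the imputed end.

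**The case against.** The strongest reply is that a negative value needs several things at once: onset after the last visit, the event recorded, no end date, and no later visit of any kind. The documents work against that combination:
- Protocol 2.1 asks subjects who leave early to attend an early termination visit.
- Unscheduled visits are entered in the eCRF, and Protocol 10.5 takes exacerbation history at them. The SAP wording is not confined to scheduled visits.
- Protocol Section 11 requires adverse events, which include worsening of a pre-existing condition, to be followed to resolution, stability or loss to follow-up. That may often supply an end date.

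All of this stands, and it makes the negative case uncommon. It does not exclude it, because an early termination visit can only be requested. Nor does it answer the second problem, since an event unresolved at an attended final visit is still counted as complete.

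It is also fair that duration is not a listed endpoint and that the study is descriptive. SAP 8.1.10 names no statistic for duration, so the mean comes only from SAP 6.1.

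SAP 10.3 points to Section 6.3 for date imputation. That section is not visible, and redacted text follows 8.1.10. A general guard could exist in either place, although the visible text of 8.1.10 refers to none.

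A reader might infer more than the documents support:
- *Bias towards EQ001.* The same rule applies to pooled placebo and every EQ001 group. It shortens durations wherever such events occur, and nothing shows which arm would have more.
- *Duration as the section's only information on burden beyond counts.* The section also summarises the primary criterion for each event, and under Protocol 10.5 the criteria range from a sustained peak-flow fall to an emergency visit or hospitalisation.
- *Unresolved events as the longest ones.* The documents do not show this. An event can be unresolved simply because it began just before the last visit.

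**Conclusion.** The point holds as a minor defect in a stated rule. An event that starts k days after the last attended visit, with no later visit, is assigned 1 - k days. That is zero or negative for every k of 1 or more, with a floor of -12 days in the 14-day gaps and -26 days between Day 57 and Day 85. Other events unresolved at the last visit are reported as complete, and so understated by an unknown amount.

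The consequence is confined to the additional duration summary. The safety endpoints, the annualized rate and the time to first exacerbation are untouched. The formula results follow from the SAP text on nominal visit days. The shift in a mean from 7.2 to 5.2 days rests on assumed data and shows only how one event could act in a small group. The conclusion also assumes that no guard in unseen SAP text overrides 8.1.10.

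**What to change.** Replace the imputation sentence in SAP 8.1.10 with a rule on these lines:

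1. For an exacerbation without an end date, use the latest date on which exacerbation information exists (last contact, diary entry or visit, including early termination and unscheduled visits), and never a date before onset.
2. Flag that duration as censored in the dataset and the listing.
3. Summarise duration for resolved events only, and show beside it, by group, the number ongoing at study exit. Do not average imputed and observed durations together.

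The count in step 3 matters because a resolved-only summary is itself selective. A Kaplan-Meier median is not proposed: with about 6 EQ001 subjects per cohort and repeat events counted separately, it may often not be estimable and would treat events in one subject as independent.

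If Section 6.3 already prevents an end date before onset, a cross-reference would cover that part of step 1. Steps 2 and 3 would still be needed.

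The cost is one SAP paragraph and a small programming change on dates already collected. The downside is that some events appear as ongoing instead of with a single duration.
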